11.3 Relevant Protocol Deviations

Relevant protocol deviations considered to have a potential impact on the primary or key secondary efficacy endpoint assessments are:

- Failure to meet any one or more inclusion criteria that define the patient population
- Failure to adhere to concomitant medication restrictions affecting the primary endpoint
- Poor compliance to study medication, i.e. overall compliance <75% for treatment period up to Week 32
- Mis-dosed (treated dose not equal randomized dose)

The detailed relevant protocol deviation criteria will be listed in [Appendix 5](#).

11.4 Exposure

Summaries of extent of study drug exposure will be provided for the all-treated population.

11.4.1 Duration of Exposure

Duration of treatment will be calculated using the date of first dose of study drug and the date of last dose of study drug as recorded on the eCRF. Duration of treatment, in days, will be calculated according to the below formula:

$$\text{Date of last dose of study drug} - \text{date of first dose of study drug} + 1$$

Duration of treatment will be reported by treatment group using summary statistics.

11.4.2 Summary of Dosing

A single dose is defined as the randomized treatment dose. Subjects are to take a total of 8 capsules per day to equal one dose.

The total number of doses taken for each subject will be determined as the following:

$$\text{Doses taken} = (\text{number capsules dispensed} - \text{number of capsules returned}) / 8$$

The total number of doses taken will be reported using summary statistics by treatment group.

11.4.3 Compliance

Treatment compliance will be determined from data captured in the eCRF.

The number and percentage of subjects who have missed at least one dose will be provided by treatment group. Additionally, summary statistics for the number of missed doses within each analysis visit period and overall will be provided by treatment group. The number of missed doses for each subject will be calculated as the following:

$$((8 \times \text{number of days in the analysis visit period}) - (\text{Number of capsules given} - \text{number of capsules returned})) / 8$$

Overall compliance will be calculated based on eCRF data as specified below.

Sponsor: Bristol-Myers Squibb
Protocol no: IM011021

1. Number of doses taken = (number capsules dispensed – number of capsules returned)/8
2. Number of expected doses taken = last dose date – first dose date + 1
3. Compliance = (Number of doses taken / Number of expected doses taken) * 100

If a subject does not return the container, then this dispensation event will be excluded in the calculation for the total number of doses taken, total number of expected doses, and total compliance. Overall compliance for the treatment period up to the Week 32 and up to Week 48 will be reported using summary statistics by treatment group and for the combined treatment groups. The number and percentage of subjects with <75%, 75% to 100%, and >100% compliance will be reported.

11.5 Prior and Concomitant Medications

Prior and concomitant medications will be coded according to World Health Organization-Drug Dictionary WHO-DD (June 2017 DDE HD B3 or an updated version at the time of database lock (DBL)) and will be summarized by Anatomic Therapeutic Classification (ATC) level 1, level 2 and preferred term (PT) by treatment group for the randomized population. The number and percentage of subjects using each medication will be displayed by treatment group. Subjects taking more than one medication within the same ATC level and/or PT will be counted once. Details of prescribing information will be provided in a listing.

Medication dates will be imputed according to algorithms detailed in [Appendix 3](#). The imputed dates will be used to assess whether medications should be included in the summaries as prior or concomitant, however the original, partial dates will be included in data listings.

Only medications collected in the study database from first dose date of IP up to last dose day of IP or up to first dose day of study IM011-074 for roll over subjects will be summarized for concomitant medications.

11.5.1 Prior Corticosteroid Use

Prior systemic CS medications (prednisone or equivalent) will be summarized as described above for the number and percentage of subjects using each CS medication. A summary of other prior medications used for SLE may also be presented.

The list of used CS medications to be selected for analyses is available in [Appendix 6](#) of the protocol.

Prior corticosteroid use data will be taken from the Prior and Concomitant Medications CRF form.

11.5.2 Concomitant Corticosteroid Use

Concomitant oral CS medications (prednisone or equivalent) will be summarized as described above for the number and percentage of subjects using each CS medication as well as continuous summaries of CS dose. The frequency and percentage of successful CS tapering and maintenance (defined as CS dose \leq 7.5 mg/day prednisone or equivalent by Week 20 continuing through Week 32 and no CS rescue therapy) will be presented by treatment group as well a summary of the reasons CS was not reduced; due to a new or worse BILAG grade, a new or worse SLEDAI-2K score, new or worse hemolytic anemia, a CLASI-A score of at least 10, a tender and swollen joint count of at least 8, or others as collected on the Corticosteroid Dose Log CRF and Steroid Taper CRF forms. The need for CS rescue will be summarized with percentages of bursts \leq 1 or $>$ 1. A listing will provide details of CS therapy use throughout the study. A blinded review of the corticosteroid use will be conducted to assess whether a subject received a CS burst. The logic for the determination of a CS burst and a spreadsheet with the CS bursts identified will be saved in the eTMF. This spreadsheet will be used for programming of CS bursts.

Sponsor: Bristol-Myers Squibb
Protocol no: IM011021

The list of used CS medications to be selected for analyses is available in [Appendix 6](#) of the protocol. Concomitant corticosteroid use data will be taken from the Corticosteroid Dose Log CRF forms.

11.6 Medical History

General medical history and medical history related to SLE will be coded using the Medical Dictionary for Regulatory Activities (MedDRA) (an updated version at the time of DBL). General medical history data will be summarized for each SOC and PT by treatment group and overall for the randomized population. Separate tables will be provided for general medical history and medical history related to SLE. Details of medical history will be provided in a listing. Medical history data will be taken from the General Medical History CRF.

Additionally, BILAG SLE history (captured at screening) will be summarized for each body organ system by treatment group and overall for the randomized population.

11.7 Efficacy Analyses

All efficacy analyses will be performed using the randomized population.

The final statistical analysis will be performed at the end of study after all subjects have completed their end of study visit (or discontinued early from the study).

Separate methods will be used for binary, continuous, time-to-event and categorical efficacy endpoints.

Subjects listings will report all collected efficacy endpoints over time until study end or early study discontinuation, regardless of treatment discontinuation before the study end or discontinuation.

Binary endpoints for analysis are:

- SRI(4) [REDACTED]
- BICLA response
- LLDAS response
- CLASI-A response

Continuous endpoints for analysis are:

- Change from baseline in the 40-joint count for tender joints, swollen joints, and joints that are both tender and swollen (= active joints)
- Global BILAG-2004 score

Categorical endpoints:

[REDACTED]

Sponsor: Bristol-Myers Squibb
Protocol no: IM011021

11.7.1 Primary Endpoint

The primary efficacy endpoint is the proportion of subjects who have a SRI(4) response at Week 32 as per non-responder imputation. All subjects in the randomized population will be categorized as a responder or non-responder.

Definition of Endpoint

A responder is defined as meeting all of the following criteria. If one criterion is not met, the subject will be considered a non-responder.

- Reduction from baseline of ≥ 4 points in the SLEDAI-2K

The total SLEDAI-2K score is the sum of the scores for all items. The total score will be taken from the eCRF. A reduction in at least 4 points is achieved if SLEDAI-2K at Week 32 – SLEDAI-2K at baseline ≤ -4 .

- No new BILAG A (severe disease activity) and not more than 1 new BILAG B (moderate disease activity) organ domain grade

An A grade is new if the baseline grade for the same organ system was B, C, D or E. A B grade is new if the baseline grade for the same organ system was C, D, or E.

This criterion is met if both of the following conditions are met:

- All organ domains with an A grade at Week 32 were graded A at baseline
- The number of organ domains with a B grade at Week 32 that were graded C, D, or E at baseline is ≤ 1

- No worsening from baseline in the Physician's Global Assessment of Disease Activity scale by at least 0.3 points
 - Physician's Global Assessment of Disease Activity at Week 32 – Baseline Physician's Global Assessment of Disease Activity < 0.3

Non-Responder Imputation (NRI) Method

Subjects will be considered non-responders at a given time point per imputation (i.e. regardless of observed SRI-response as defined above) if any of the following apply:

- Subject takes any of the following prohibited medications:
 - Corticosteroid dosages above 7.5mg/day prednisone or equivalent after week 20 (Week 20+1 day)
 - Use of IM or IV CS within 8 weeks before the W32 assessment timepoint
 - Use of IA or intrabursal CS within 8 weeks before the W32 assessment timepoint

Sponsor: Bristol-Myers Squibb
Protocol no: IM011021

- Use of modified-release oral CS formulations within 8 weeks before the W32 assessment timepoint
- Addition (compared to baseline) of topical CS within 2 weeks before the W32 assessment timepoint
 - Ocular CS are allowed for non-SLE indications
 - Inhaled CS are allowed
- CS bursts/rescue above the protocol-defined maximum dosage (40 mg/day prednisone equivalent)
- More than 1 CS burst or any CS burst for treatment of SLE after week 8
 - Oral steroid burst for non-SLE indication is permitted up to week 24 or between week 32 and week 40
- Initiation of or increases in oral NSAIDs (compared to baseline) occurring within the 7 days before the W32 assessment timepoint
- Initiation of or increase in immunosuppressant dosage/regimen and/or antimalarial dosage/regimen (compared to baseline)
 - Dose decrease or discontinuation is permitted
 - Discontinuation with subsequent restart at the same or lower dose is permitted
 - Immunosuppressants are defined as (combinations of these are not permitted): Azathioprine, 6-MP, methotrexate, leflunomide, MMF
 - Antimalarials are defined as: chloroquine, hydroxychloroquine, or quinacrine
- Subjects takes any medications included in protocol Appendix 7 between first dose date and efficacy assessment visit
- Permanent treatment discontinuation of IP before the considered time point
- Missing value for the endpoint at the considered time point
- Subjects who are lost to follow-up or discontinue the study early are considered non-responders for all time points at and after loss to follow up or study discontinuation

Primary Analysis

The primary analysis will be conducted on the randomized population.

The analysis of NRI-imputed SRI(4) response at Week 32 will be conducted using logistic regression modeling, with treatment group (four levels) and redefined stratification factor (see [section 6.5](#), thirteen levels) as fixed factors. The odds ratios of response will be estimated and tested between the BMS-986165 treatment groups and the placebo group [REDACTED]. In case the logistic regression model fit is not stable the region stratification factor may be removed from the model (resulting in 5 stratification factors: non-Japan subjects with baseline CS dose ≥ 10 mg/day and SLEDAI-2K score ≥ 10 , non-Japan subjects with baseline CS dose < 10 mg/day and SLEDAI-2K score ≥ 10 , non-Japan subjects with CS dose ≥ 10 mg/day and SLEDAI-2K score < 10 , non-Japan subjects with CS dose < 10 mg/day and SLEDAI-2K score < 10 and Japan subjects). Estimated odds ratios of response with corresponding 2-sided 95% confidence interval (CI) and p-value will be reported.

The number and percentage of subjects achieving NRI-imputed SRI(4) response at Week 32 and those who do not will be reported by treatment group with the estimated response rate and asymptotic 95% confidence intervals (CIs). Differences in response rates between each active treatment group and placebo with corresponding 2-sided 95% CIs based on the continuity-corrected Newcombe method will also be provided.

Tipping Point Analysis

Tipping point analysis will further be used to assess the robustness of the primary study results. Different number of events between treatment groups will be assessed until the study conclusion is

Sponsor: Bristol-Myers Squibb
Protocol no: IM011021

changed. Each imputed value is initially imputed as a responder. The imputed values in the placebo group will remain as responders while the BMS-986165 imputed values are replaced as a non-responders one at a time, therefore changing the number of events between groups. Once all imputed values in the BMS-986165 group have been replaced with non-responders values, the data will reset to where the BMS-986165 group imputed values are all responders and one by one the imputed values in the placebo group are replaced with a non-responder until all placebo are non-responders and all BMS-986165 are responders. Furthermore, every pair of imputations between the placebo and BMS-986165 groups will be assessed similarly, creating a matrix of possible patterns.

At each iteration, the statistical analysis is assessed, and the direction of the analysis is recorded. A graph will be provided to identify at what point to which the difference in events cause a direction shift in study results. The tipping point analyses will be based on a two-sample chi-square test approach rather than a stratified CMH test approach for simplicity of the analysis.

Sensitivity analysis #1 (Treatment Policy Strategy)

The primary analysis for the primary endpoint will be repeated using a treatment policy estimand approach (Intention-To-Treat (ITT) principle). For this approach, subjects will only be imputed as non-responders if there is a missing value for the endpoint at the considered timepoint.

Sensitivity analysis #2

The primary analysis for the primary endpoint will be repeated, however the NRI imputation method will be modified. The prohibition medications restriction for the NRI imputation method will not apply. That is, subjects who take any of the prohibited medications listed above will not be imputed as non-responders. Subjects will continue to be imputed as non-responders if any of the following apply:

- Permanent treatment discontinuation of IP before the considered time point
- Missing value for the endpoint at the considered time point
- Subjects who are lost to follow-up or discontinue the study early are considered non-responders for all time points at and after loss to follow up or study discontinuation

Supportive Analysis #1 – Assessment of Covid-19 related impact

For this supportive analysis, the primary analysis for the primary endpoint will be repeated, but observations that were missed due to the impact of COVID-19 will be imputed with the last value observed before the visit that was missed due to COVID-19 restrictions.

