6.7.1 Prohibited and/or Restricted Treatments

Restrictions and prohibitions on prior and concomitant medications are as follows:

1. Prior exposure to BMS-986165 or other TYK2 inhibitors is prohibited.
2. Rescue therapy other than prednisone or equivalent is prohibited.

3. Use of intramuscular, intra-articular, intrabursal, and IV CS is prohibited (Inclusion Criterion 3)b); [Section 5.1](#)). Initiation during the study of short-term treatment with inhaled CS for a nonlupus medical condition must be discussed with the [REDACTED] medical monitor. Topical CS use may not be initiated during treatment. Modified-release CS formulations are prohibited.
4. Topical NSAID use may not be initiated during treatment. No more than 1 oral NSAID may be used during the study. Aspirin is allowed (in addition to a single NSAID and topical NSAIDs) at stable doses no higher than 325 mg/day throughout the study. NSAIDs may not be used on an as-needed basis. Although regimens are required to be stable throughout the study, NSAID dosing may be decreased or discontinued if due to NSAID toxicity. Adjustments in NSAID regimens must be discussed with the [REDACTED] medical monitor.
5. Use of opioid analgesics is prohibited unless criteria outlined in Exclusion Criterion 3)e); [Section 5.2](#), are met.
6. Use of cyclophosphamide (including ophthalmic) or any IV, intrabursal, intratendinous sheath, intramuscular, subcutaneous, intra-articular, or biologic agent is prohibited. Required discontinuation periods for immunomodulatory and biologic drugs before the signing of informed consent are provided in [APPENDIX 7](#). For similar agents not listed, the discontinuation period is 4 weeks or 5 half-lives, whichever is longer, and must be discussed with the [REDACTED] medical monitor.
7. Live vaccines are prohibited during the TP or within the 2 months after the last dose. Heat-killed or otherwise inactivated or protein vaccines such as influenza and pneumococcal vaccines may be received at any time on study. Any other inactivated vaccines (eg, tetanus, etc) should be used according to local guidelines during the TP (Exclusion Criterion 4)g); [Section 5.2](#)).
8. Exposure to any investigational drug or placebo within 12 weeks or 5 half-lives (whichever is longer) before screening is prohibited (Exclusion Criterion 3)f); [Section 5.2](#)

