 - Use of IA or intrabursal CS within 8 weeks before the W32 and W48 assessment timepoints
 - Use of modified-release oral CS formulations within 8 weeks before the W32 and W48 assessment timepoint
 - Addition of topical CS within 2 weeks before the W32 and W48 assessment timepoint
 - Ocular CS are allowed for non-SLE indications
 - Inhaled CS are allowed

- More than 1 CS burst or any CS burst for treatment of SLE after week 8

Sponsor: Bristol-Myers Squibb
Protocol no: IM011021

- Oral steroid burst for non-SLE indication is permitted up to week 24 or between week 32 and week 40
- Initiation of or increases in oral NSAIDs occurring within the 7 days before the W32 and W48 assessment timepoints
- Initiation of or increase in immunosuppressant regimen and/or antimalarial dosage/regimen
 - Dose decrease or discontinuation is permitted
 - Discontinuation with restart at the same or lower dose is permitted
 - Immunosuppressants are defined as (combinations of these are not permitted): Azathioprine, 6-MP, methotrexate, leflunomide, MMF
 - Antimalarials are defined as: chloroquine, hydroxychloroquine, or quinacrine
- Any medications included in protocol Appendix 7 between first dose date and efficacy assessment visit

Similar analyses will be conducted as for the primary endpoint, including the primary analysis and sensitivity analysis.

11.7.2.3 CLASI-A Response (CLASI-50) at Week 48

Subjects who have a baseline CLASI activity score ≥ 10 will be included in this analysis. Subjects meeting this criterion will be categorized as CLASI-A responders or non-responders. Responders are defined as subjects who have at least a 50% decrease in their CLASI activity score at Week 48.

$$\frac{\text{CLASI activity score at Week 48} - \text{CLASI activity score at baseline}}{\text{CLASI activity score at baseline}} \times 100 \leq -50$$

Subjects not meeting this criterion will be considered non-responders.

Similar analyses will be conducted as for the primary endpoint, including the primary analysis and sensitivity analysis.

11.7.2.4 LLDAS Response at Week 48

A subject is considered an LLDAS responder at Week 48 if all of the following criteria are met:

- SLEDAI-2K ≤ 4 , with no activity in major organ systems (renal, central nervous system, cardiopulmonary, vasculitis, fever) and no hemolytic anemia or gastrointestinal activity (measured as maintaining a D or E score in the BILAG gastrointestinal body system)

This definition will be implemented as follows:

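### The non-responder items for oral NSAIDs and, less clearly, topical corticosteroids key on the date the drug was started, so a subject still taking one started earlier is not imputed

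*SAP*

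**What the plan says.** SAP 11.7.1 lists the medication events that turn a subject into a Week 32 SRI(4) non-responder whatever response was observed. The lead-in is "Subject takes any of the following prohibited medications". Two items matter here:

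- Oral NSAIDs: "Initiation of or increases in oral NSAIDs (compared to baseline) occurring within the 7 days before the W32 assessment timepoint".
- Topical corticosteroids (CS): "Addition (compared to baseline) of topical CS within 2 weeks before the W32 assessment timepoint".

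SAP 11.7.2.2 carries both into the BICLA definition. Its NSAID item reads "Initiation of or increases in oral NSAIDs occurring within the 7 days before the W32 and W48 assessment timepoints".

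Other items in the 11.7.1 list are built differently. Injected steroids are defined by use, for example "Use of IM or IV CS within 8 weeks before the W32 assessment timepoint". The immunosuppressant and antimalarial item counts any start or increase over baseline, with no window.

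Protocol 6.7.1 says "Topical CS use may not be initiated during treatment" and, for NSAIDs, "Although regimens are required to be stable throughout the study, NSAID dosing may be decreased or discontinued if due to NSAID toxicity". Protocol 9.3.1.2 treats a subject who needs a medication prohibited under 6.7.1 or Appendix 7 as a non-responder, with no look-back window.

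**The concern.** In the NSAID item the thing that must fall inside the 7 days is the initiation or increase. The topical CS item has the same structure, although it is less explicit. A sustained new exposure that began before the window therefore passes, and a shorter one that began inside it fails. That is the reverse of what a rule against confounding co-medication should do.

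The items bear on the primary endpoint directly. In the SLEDAI-2K (protocol Appendix 11), arthritis carries 4 points, which is the whole reduction SRI(4) requires, and rash carries 2. The same criteria decide which joint counts are set to missing in the repeated-measures model of SAP 11.7.2.5. If new co-medication helps a subject meet the response criteria and the rule does not see it, the response is credited to the randomized arm.

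**Working it through.** The plan gives no rate of new NSAID or topical CS use, so it has no figure to reproduce. The check applies the rule as written, compares it with the protocol and the other planned analyses, and then shows a range under stated assumptions.

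**1. Which start days are flagged.** The Week 32 target is Day 225 (SAP 7.2). Take a drug started on day *s*, after Day 1 and before the visit, and still taken on Day 225. There are 224 − 2 + 1 = 223 possible start days (Days 2 to 224). With window *w*, the wording flags the subject only if 225 − *w* ≤ *s* < 225.

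| Item | *w* | Start days flagged as written | Flagged by a use-based rule |
|---|---|---|---|
| Oral NSAID | 7 | Days 218-224: 7 of 223 | 223 of 223 |
| Topical CS | 14 | Days 211-224: 14 of 223 | 223 of 223 |

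For example, an NSAID started on Day 197 (Week 28) and still taken at Week 32 is not flagged; one started on Day 219 is. These are counts of days, not shares of patients, because nothing in the documents says how starts are spread over time.

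**2. Whether anything else catches these subjects.**

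- Protocol Appendix 7 lists neither NSAIDs nor topical CS, so the SAP item that refers to it does not help. The steroid dose and burst items do not address topical CS.
- Sensitivity analysis #1 imputes only missing values. Sensitivity analysis #2 drops the medication rule. Both are looser than the primary rule.
- The tipping-point analysis varies only imputed values, and these subjects are not imputed.
- Per-protocol analyses were removed (SAP 5.4.2).
- The relevant-deviation list in SAP Appendix 5 refers back to the 11.7.1 list and inherits its wording.

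**3. Illustrative size.** Assumptions, none from the documents: true response 40% on placebo and 60% on active; 3-8% of placebo and 1-4% of active subjects on a newly started agent at Week 32; half of them wrongly counted as responders. Observed rate = true rate + 0.5 × share on the agent.

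| Placebo share | Active share | Observed placebo | Observed active | Difference |
|---|---|---|---|---|
| 3% | 1% | 41.5% | 60.5% | 19.0 points |
| 8% | 4% | 44.0% | 62.0% | 18.0 points |
| 8% | 1% | 44.0% | 60.5% | 16.5 points |
| 3% | 4% | 41.5% | 62.0% | 20.5 points |

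The difference moves by 0.5 × (active share − placebo share), so its direction depends only on which arm has more such use.

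**4. What the look-back does.** SLEDAI-2K scores manifestations present at the visit or in the preceding 30 days. For a Day 225 visit that reaches back to 225 − 30 = Day 195. If arthritis was active when an NSAID was started on or after Day 195, it can still be scored at Week 32. Starts before Day 195 have no such protection, and the wording flags none of them.

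**The case against.** **The wording may be meant as use.** The lead-in speaks of what the subject takes, and both items compare with baseline, which suggests comparing regimens. The SAP 5.5 change log records a deleted allowance for initiations or increases lasting under 4 days, so the authors may have thought of an initiation as a period of new use. The topical CS line has no word tying the date to the start. This stands as a reason for calling that item ambiguous. It does not rescue the NSAID item, which dates the initiation or increase itself in a list that speaks of use elsewhere. Two programmers could code these lines differently.

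**The effect is limited.** The 30-day look-back protects against late starts, and protocol 8.1 requires NSAIDs to be withheld for at least 12 hours before efficacy visits. Both points stand for starts shortly before the visit. Neither removes the gap for earlier starts, and the NSAID hold does not apply to topical CS.

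**Such starts should be few.** They generally run against protocol 6.7.1. However, NSAID stability is not absolute: inclusion criterion 3)c) allows exceptions with the medical monitor's approval. The number affected is unknown, which limits the severity but does not make the wording sound.

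**A stronger reading.** A reader might infer that placebo subjects start these drugs more often, so the rule dilutes the effect and costs power. The documents give no usage rates by arm, and one corner of the table above widens the difference. A power loss worked from a single dose against placebo (74% at 90 per arm, 40% versus 60%, two-sided 0.04) would also not start from the trial's own figure. The plan states at least 84% for the BID arms, with the placebo rate and exact test redacted.

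**Conclusion.** The concern holds as a defect of wording and of consistency with the protocol. Read as written, the NSAID item, and less clearly the topical CS item, misses a drug started before the window and still in use at the visit. The SAP is therefore narrower than protocol 9.3.1.2, without a stated reason, and no planned analysis is stricter. The conflict with protocol 6.7.1 is plainest for topical CS, where starting on treatment is barred outright.

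The size and direction of the effect on the treatment difference cannot be derived from the documents. The 16.5 to 20.5 points rest wholly on the assumed usage shares, the assumed half wrongly counted, and the assumed 40% and 60% response rates. This should be fixed, but the documents do not show that it threatens the trial's conclusion.

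**What to change.** Before unblinding, reword the two items in SAP 11.7.1 and their counterparts in 11.7.2.2 so that the trigger is use within the window:

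- any use, in the 7 days before the assessment, of an oral NSAID not in use at baseline or taken at a dose above baseline;
- any use, in the 2 weeks before the assessment, of a topical CS not in use at baseline.

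That alone leaves the SAP narrower than the protocol. The sponsor should also reconcile the SAP windows with protocol 9.3.1.2 and 6.7.1, and state the reason for any difference that remains. Which medication rule is clinically appropriate is for the sponsor to settle.

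The cost is two SAP lines, repeated once, and a programming change on concomitant-medication data already collected at every visit. Patient care does not change. The downside is slightly lower response rates.
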